Sample size and power considerations. To determine sample size, we started at the right of the schematic in Figure 1 (the second randomization) and moved from right to left to determine the needed number of consenting dyads. To power the comparisons on primary outcomes for the groups created by the second randomization (Aim 2), we used the effect size of Cohen’s $d=0.39$ (adjusted for baseline), the smallest seen in the preliminary data for TIP-C against an educational intervention (Table 1) to conservatively estimate sample size requirements. We further adjusted this effect size for the reduction in error variance due to 10 repeated measures of primary outcomes. In past studies, Pearson correlation coefficients between pairs of repeated measures of depression, anxiety and summed severity of other symptoms ranged from $r=0.36$ to 0.77, resulting in the range of the adjusted effect sizes from $d=0.54$ to 0.84. Using the smallest adjusted $d=0.54$, the required sample size is 60 per group created by the second randomization, for power of .80 or greater in two-tailed tests at the 0.05 level of significance.

Moving from left to right in Figure 1 (schematic), 120 dyads from two groups created by the second randomization will be non-responders to the SMSH alone. From past work, response rate to the SMSH on depression and anxiety was approximately 30%,²²⁸ therefore 120 non-responders will be 70% of 172 randomized to the SMSH alone in the first randomization. The comparison of these 172 to 60 dyads allocated to the TIP-C+SMSH in the first randomization will have power of 0.95 to detect the effect size of 0.54 (adjusted for the repeated measures) in testing the hypothesis associated with Aim 1. The tests of mediation and interdependence effects in Aim 3 will have an even greater power because of further reduction in error variance. Aim 4 is exploratory, thus formal power considerations are not applicable. In summary, the total

required post-attrition sample size for all specific aims is N=232. To account for 22% attrition based on past work, we will need 298 dyads to consent.

Recruitment and retention of participants.

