Randomization. Following the baseline interview, dyads will be randomized to either SMSH alone (N=172 post-attrition) or to TIP-C+SMSH (N=60 post-attrition). A minimization algorithm will be programmed by [name] to balance arms by recruitment location, site of cancer, stage of cancer (early versus late), type of treatment, and survivor's relationship to the caregiver (spouse vs non-spouse).²³⁹ The second randomization will occur for those who do not respond to the SMSH alone after the first 4 weeks using the same approach as the first randomization except in 1:1 ratio. The study coordinator will run the computer algorithm from the main study office (Tucson) to ensure allocation, concealment, and blinding.

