Aim 1, Hypothesis 1: Dyads initially randomized to the TIP-C+SMSH will report lower depression, anxiety, and summed severity of other symptoms at weeks 1-12, 13, and 17, and lower unscheduled health services use, higher self-efficacy and social support, and lower caregiver burden at weeks 13 and 17 as compared to those initially randomized to the SMSH alone. This hypothesis will be tested using statistical model #1 that relates repeated measures of the survivor or caregiver outcome y (one at a time) to the group assignment variable xx_1 , outcome at baseline xx_2 , time entered as a class variable to model potentially non-linear patterns, and other covariates. For normally distributed outcomes, this model will be fit as a linear mixed effects model (LME). Generalized linear mixed effects (GLME) modeling will be used if outcome is not normally distributed and cannot be normalized using transformations. For health service use, statistical model #1 will be implemented as a GLME model with Poisson distributed errors, or as a zero-inflated Poisson or negative Binomial model based on the distribution of the counts of different health services uses. Each type of health services use (e.g., hospitalizations, ED visits) will be analyzed separately. The explanatory variables including study group will be evaluated as predictors of zero inflation (whether or not the count is zero), and also as predictors of the magnitude of the count when it is not zero. The main effects of the group variable xx_1 will be tested.

Aim 2, Hypothesis 2: Dyads where survivors do not respond to the SMSH alone during weeks 1-4 and have TIP-C added during weeks 5-12, will report lower depression, anxiety, and summed severity of other symptoms at weeks 5-12, 13, and 17, and lower unscheduled health services use, higher self-efficacy and social support, and lower caregiver burden at weeks 13 and 17 as compared to those who are re-randomized to continue with the SMSH alone. The strategy described under the analyses for Aim 1 will be implemented for the repeated outcome measures during weeks 5-12 and weeks 13 and 17 that will be related to group assignment from the second randomization, symptom severity during week 4, time, and covariates.

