| 8 | Termination of counseling, review successes, reviews social support, stress and coping strategies. Future planning recommendations for follow-up treatment (e.g. antidepressants or continued counseling), framing successes and failures. Discuss options and referrals as needed. Resources available locally and nationally for survivors and their families, including financial, insurance ¹⁷² and legal information ¹⁷³ (session slightly longer). |

Telephone Interpersonal Counseling Intervention (TIP-C). Social work counselors with a master's degree and behavioral health and oncology expertise will deliver the 8-week TIP-C intervention (Table 2).

During weekly contacts, the counselors target social support behaviors using interpersonal communications techniques. Interpersonal communication facilitates processing stressful affective reactions to a cancer diagnosis and treatment, marshalling instrumental support for assistance with roles and functions, informational support for advice and information, and appraisal support for gauging and adjusting to the stressor. Counselors can personalize the counseling intervention for the specific needs or interests as expressed during sessions while still adhering to a structured protocol. For example, one survivor may need to focus on depression and family issues (e.g., role transitions such as job loss) rather than on anxiety and resource issues (e.g., transportation, lack of insurance). This approach is consistent with survivorship care recommendations²⁴¹ and recent evidence showing that improved psychological well-being occurs when an intervention addresses practical resource needs.²⁴²

Each survivor and caregiver receiving the TIP-C+SMSH intervention will receive one 40-minute telephone call per week for 8 weeks (8 sessions). The first 10 minutes of the call will follow the SMSH only intervention procedures (see C8c). The next 30 minutes will be devoted to the delivery of TIP-C. The TIP-C sessions will incorporate the symptoms assessment performed at the beginning of the call as follows: discussion of depression, anxiety and stress per protocol and referral to the SMSH for symptoms. The final 4 weeks will be SMSH only. The TIP-C intervention protocol is the same for both survivor and caregiver, the same counselor will be assigned to both members of the dyad and sessions conducted in either Spanish or English.

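### Model #1 has no counselor term although TIP-C dyads are nested in counselors; in Aim 2, where only one group receives TIP-C, any positive counselor ICC makes the standard error too small

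*Combined protocol and SAP*

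**What the plan says.** Section 7.0 has master's-level social work counselors deliver eight weekly TIP-C sessions, and "the same counselor will be assigned to both members of the dyad". Content may vary within a structured protocol: "Counselors can personalize the counseling intervention for the specific needs or interests as expressed during sessions". A counselor whose adherence is below 90% receives no new cases until retrained, and the existing cases pass to someone else. The number of counselors is not given. SMSH calls are made by staff who are not further described.

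The analysis appears in Section 5.0 and again in Section 8.0: "This hypothesis will be tested using statistical model #1 that relates repeated measures of the survivor or caregiver outcome" to group, baseline outcome, time as a class variable and other covariates. Aim 2 uses the same strategy, with week-4 severity and the second-randomization group. No counselor effect is named in the model, in the list of potential covariates or in the sample size section.

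For Aim 2, Section 4.0 states that "the required sample size is 60 per group created by the second randomization". The target behind that number is at least 80% power with two-sided testing at 5%. For Aim 1 it states: "The comparison of these 172 to 60 dyads allocated to the TIP-C+SMSH in the first randomization will have power of 0.95", at an effect size of 0.54. Non-responders to SMSH alone are re-randomized "using the same approach as the first randomization except in 1:1 ratio".

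**The concern.** Dyads treated by one counselor share that counselor's skill and style, so their outcomes may be correlated. Section 7.0 can also be read to mean that the counselor administers the weekly GSDS in the first ten minutes of each TIP-C call. If so, an interviewer effect on a primary outcome could add to the therapist effect.

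Where only one group has counselors, the design is partially nested. A model without a counselor term treats those dyads as independent and understates the variance of the TIP-C mean. The result would be a test that rejects too often, power below the stated figure, and a risk that the effect of one or two good counselors is reported as an effect of TIP-C.

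**Working it through.** **Inputs from the documents (Section 4.0).** Two-sided alpha 0.05; d = 0.54, taken as given; Aim 2 groups of 60 and 60; Aim 1 groups of 60 (TIP-C+SMSH) and 172 (SMSH alone). With 30% response, 120 of the 172 are re-randomized 1:1, so 60 of the 172 (35%) receive TIP-C from week 5. Intent to treat keeps them in the SMSH-alone group.

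**Assumptions.** J = 3 to 6 counselors with equal caseloads, and counselor ICC ρ = 0.01 to 0.05, defined on the dyad-level outcome on which 0.54 is standardized. Total variance is 1 and critical values are normal. The SMSH callers add no clustering.

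**The plan's own figures.** Power = Φ(0.54/SE − 1.96).
- Aim 2: SE = √(1/60 + 1/60) = 0.1826, so power = Φ(2.958 − 1.96) = 0.841. This agrees with the stated .80 or greater.
- Aim 1: SE = √(1/60 + 1/172) = 0.1499, so power = Φ(3.60 − 1.96) = 0.950. This agrees with the stated 0.95.

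Both reproduce with no allowance for clustering.

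**Aim 2, TIP-C in one group only.** DE = 1 + (60/J − 1)ρ, and the SE ratio (true to modelled) is √((1 + DE)/2). For J = 3 and ρ = 0.05, DE = 1 + 19 × 0.05 = 1.95 and the ratio is √1.475 = 1.214. Actual type I error is 2(1 − Φ(1.96/ratio)).

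**Aim 1, weeks 1-4, TIP-C in one group only.** Variance = DE/60 + 1/172. For J = 3 and ρ = 0.05 this is 0.0325 + 0.0058 = 0.0383. Independence gives 0.0225, so the ratio is 1.305.

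**Aim 1, week 5 onward, TIP-C in both groups.** If the same J counselors serve both groups, their effects partly cancel. Variance = (1 − ρ)/60 + (112 + 60(1 − ρ))/172² + (ρ/J)(1 − 60/172)². For J = 3 and ρ = 0.05 this is 0.0158 + 0.0057 + 0.0071 = 0.0286, so the ratio is 1.128.

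Each cell shows SE ratio / type I error / power at d = 0.54:

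| J, ρ | Aim 2 | Aim 1, weeks 1-4 | Aim 1, week 5 on |
|---|---|---|---|
| 6, 0.01 | 1.022 / 5.5% / 0.825 | 1.033 / 5.8% / 0.937 | 1.011 / 5.3% / 0.945 |
| 4, 0.02 | 1.068 / 6.6% / 0.791 | 1.099 / 7.4% / 0.906 | 1.038 / 5.9% / 0.934 |
| 4, 0.05 | 1.162 / 9.2% / 0.721 | 1.232 / 11.2% / 0.832 | 1.093 / 7.3% / 0.909 |
| 3, 0.05 | 1.214 / 10.7% / 0.683 | 1.305 / 13.3% / 0.788 | 1.128 / 8.2% / 0.891 |

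The first and last rows are the mildest and worst corners of the assumed range. The Aim 1 group effect is assessed over 14 post-baseline occasions: 4 in weeks 1-4, and 10 later (weeks 5-12, 13 and 17). The last column therefore describes most of the Aim 1 data. None of these power figures includes the further loss from estimating a counselor variance with few counselors.

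**The case against.** The strongest reply is that the plan is silent rather than wrong. Model #1 allows other covariates and does not list its random effects, so a counselor term is unspecified, not excluded. That is fair, but a term left unspecified would have to be chosen after the data are seen, and the power calculation leaves no room for it.

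Second, training to criterion, the 90% adherence rule, weekly supervision, review of about 10% of sessions, and retraining or replacement are all meant to make counselors alike. Personalization follows the participant's needs, so it does not in itself show that dyads sharing a counselor resemble each other. This stands: these provisions are no evidence that the ICC is large. They may reduce counselor variation, but they do not measure or model it.

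Third, the size rests on assumed inputs. With 10 counselors and an ICC of 0.01, the Aim 2 inflation is only 1.2% and type I error 5.3%; at an ICC of zero there is none. The SMSH callers may also cluster, which these figures ignore.

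Two stronger readings are tempting. A reader might infer that TIP-C is confined to one group in both comparisons. The documents contradict this for Aim 1: after week 4 half of the SMSH-alone non-responders add TIP-C and stay in their original group. A reader might also infer that there are few counselors and that type I error certainly exceeds 5%. The documents give no counselor count and no ICC, so both statements are conditional.

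**Conclusion.** The point holds, chiefly for Aim 2. Counselors take whole dyads, only one of the two groups receives TIP-C, and neither the stated model nor the sample size allows for this. The direction of the error is certain for any counselor ICC above zero; its size is not. Over the assumed range the Aim 2 inflation runs from minor to serious. At 4 counselors and an ICC of 0.02, power is already just under 0.80.

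Aim 1 is affected less. Its one-sided figures apply only to weeks 1-4. The smaller week-5 figures (1% to 13% inflation, type I error 5.3% to 8.2%) require that the same counselors serve both groups, on which the documents are silent. Specifying the term before analysis is worthwhile, but the documents do not show that the trial's conclusions would be wrong without it.

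**What to change.** 1. State the number of counselors, and record counselor ID for every TIP-C dyad, including dyads stepped up after week 4 and any takeover from a non-adherent counselor. Assign each dyad to its first counselor, and repeat the analysis using the counselor who delivered most sessions.
2. For Aim 2, add to the model a counselor random intercept that applies only to dyads receiving TIP-C, with small-sample degrees of freedom such as Kenward-Roger.
3. For Aim 1, apply the same term to TIP-C recipients in both groups from the week their TIP-C starts.
4. Add a sensitivity analysis with the counselor ICC fixed at 0.01, 0.02 and 0.05, because the variance may be poorly estimated. State which variance the ICC refers to.
5. Show power over a stated range of ICC and counselor numbers.

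The cost is SAP wording, one ID field and one random term. Counselors already write field notes after each session, so the link to dyads should be recoverable. The statistical cost is wider intervals and fewer degrees of freedom. With 3 to 6 counselors the variance component rests on only 2 to 5 degrees of freedom, and with 3 or 4 counselors the loss of precision could be material.

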8.0 STATISTICAL CONSIDERATIONS

Analysis Plan for answering objectives including endpoint definitions, patient accrual objectives, and estimated duration of study. This section should be developed in consultation with appropriate biostatistician.

Potential Covariates and Future Tailoring Variables. These variables will be assessed during baseline interviews of survivors and caregivers. Demographic characteristics include caregivers' and survivors' age, education, work, ethnicity, race, acculturation, marital status, relationship between survivor and the caregiver, and living arrangement. Comorbidity will be measured with the Bayliss tool that queries the presence of 20 comorbidities,²⁵⁸ and we will also collect height and weight to calculate BMI. The validity and reliability of self-reported height and weight are adequate²⁵⁹⁻²⁶¹, and health risk estimates associated with BMI values are virtually the same, whether based on self-report or measured BMI values.²⁶² Caregiver's activities of survivor care will be measured using a checklist¹⁹, and quality of relationship will be measured using a 6-item index designed to assess the relationship quality. The index has established reliability with samples of married couples²⁶³ and has also been used to capture survivors' perceptions of the quality of relationship with their friend/family caregiver. Preferred language of intervention delivery will be tracked. Receipt and enactment of intervention strategies are measured during weeks 1-12. Receipt will be measured by the number of completed weekly sessions. Enactment of the SMSH strategies is assessed at the beginning of calls during weeks 2-12 as described in section C8c. Enactment of the TIP-C will be measured by tracking the implementation of behaviors discussed and completion of the assigned homework as documented in counselor's field notes for each session. Assessment of survivors' radiation, surgery, chemotherapy, targeted or hormonal therapy (dose, type, dates received), cancer site and stage, and medications (e.g., supportive agents for symptoms) will be collected from health record data corresponding with the time-on-study. Every effort has been made to keep respondent burden to a minimum and to distribute any burden over the course of the study. If needed, we can divide the assessments into two sessions over two days. Yet, few participants requested such accommodations in past studies.

Scientific Rigor and Transparency. The scientific rigor of this study is ensured by the randomized design, complete inclusion/exclusion criteria defining the population to which findings would be generalizable, reproducible manualized protocol for the interventions, tracking of intervention fidelity, dose, receipt and enactment, use of measures with solid evidence of reliability and validity, blinding of data collectors, transparent assessment and statistical analysis plans including attention to biases and the missing data.

Sex as a biological variable. We will consider survivors' and caregivers' sex as covariates in all analyses. Past research indicates that the survivor-caregiver relationship (spouse/partner versus other) is a key factor that may influence outcomes^{62,165} for the dyad over and above sex. Relationship will be controlled in randomization and considered along with sex as a covariate and potential future tailoring variable.

Analytic Methods

Data management. All data will be entered into the secure web-based database. Quarterly quality assurance checks of the data will be performed by the RA supervised by [name]. De-identified data will be transferred into SAS 9.4 for analyses. The distributions of outcomes and potential covariates will be assessed, outliers will be investigated by inspecting the residuals, and models described below will be fit with and without outliers to examine their influence on the results.

Attrition Analyses and Handling of Missing Data. We will compare dyadic characteristics of those who completed the study to those who did not within their designated group to inform the generalizability of findings. Attrition will also be compared between each pair of randomized groups. The regression techniques described below allow for missing at random (MAR) mechanism.²⁶⁴ If patterns of missing data indicate potential not missing at random (NMAR) mechanisms, then models describing missing mechanisms will be considered (e.g., pattern-mixture models),^{265,266} and sensitivity analyses will investigate the robustness of the results.

Primary Analysis. Primary analyses will follow the intent to treat approach.

Aim 1, Hypothesis 1: Dyads initially randomized to the TIP-C+SMSH will report lower depression, anxiety, and

summed severity of other symptoms at weeks 1-12, 13, and 17, and lower unscheduled health services use, higher self-efficacy and social support, and lower caregiver burden at weeks 13 and 17 as compared to those initially randomized to the SMSH alone. This hypothesis will be tested using statistical model #1 that relates repeated measures of the survivor or caregiver outcome y (one at a time) to the group assignment variable xx_1 , outcome at baseline xx_2 , time entered as a class variable to model potentially non-linear patterns, and other covariates. For normally distributed outcomes, this model will be fit as a linear mixed effects model (LME). Generalized linear mixed effects (GLME) modeling will be used if outcome is not normally distributed and cannot be normalized using transformations. For health service use, statistical model #1 will be implemented as a GLME model with Poisson distributed errors, or as a zero-inflated Poisson or negative Binomial model based on the distribution of the counts of different health services uses. Each type of health services use (e.g., hospitalizations, ED visits) will be analyzed separately. The explanatory variables including study group will be evaluated as predictors of zero inflation (whether or not the count is zero), and also as predictors of the magnitude of the count when it is not zero. The main effects of the group variable xx_1 will be tested.

Aim 2, Hypothesis 2: Dyads where survivors do not respond to the SMSH alone during weeks 1-4 and have TIP-C added during weeks 5-12, will report lower depression, anxiety, and summed severity of other symptoms at weeks 5-12, 13, and 17, and lower unscheduled health services use, higher self-efficacy and social support, and lower caregiver burden at weeks 13 and 17 as compared to those who are re-randomized to continue with the SMSH alone. The strategy described under the analyses for Aim 1 will be implemented for the repeated outcome measures during weeks 5-12 and weeks 13 and 17 that will be related to group assignment from the second randomization, symptom severity during week 4, time, and covariates.

Mediation analyses for Aims 1 and 2. To test for mediation, the study group will be treated as the independent variable, and each of the potential mediators (one at a time) will be tested for their effect on the symptom outcome variable at weeks 13 and 17, with the baseline measure of that respective symptom outcome variable treated as a covariate. Caregiver burden will be tested only at the individual level, but social support and self-efficacy will be tested at the individual and dyadic levels. We will use a bias corrected bootstrapping analytic strategy^{267,268} based on 5000 bootstrap samples to estimate confidence intervals around the indirect effect of study group on the outcome variable, through the mediator. To establish mediation, the 95% confidence interval around the indirect effect must not include 0.

Aim 3 examines the dyadic interdependence in outcomes between survivors and caregivers. This interdependence will be modeled and tested with the actor-partner interdependence mediation model (APIMem)²⁶⁹ in structural equation modeling. The APIMem estimates three classes of effects: actor effects (e.g., person A independent variable (IV) \rightarrow person A dependent variable (DV)), caregiver (partner) effects (e.g., person A IV \rightarrow person B DV), and mediation effects (e.g., person A IV \rightarrow person B Mediator \rightarrow person A DV) in an omnibus model. These models will specify correlations between the survivors' and caregivers' IVs as well as covariances between the error terms of the mediators and outcome variables, recognizing that these residuals will covary between dyad members due to unmeasured common causes. We will fit both a saturated version of the model in which all actor, partner, and mediation effects are free to vary and compare that with a constrained model in which the effects for one dyad member are constrained equal to the corresponding effects of the other dyad member. The χ^2 difference test will determine whether the more parsimonious constrained model or the unconstrained model will be interpreted. This test will also indicate whether the effect for survivors is significantly different from that of caregivers. These models will test whether baseline to week 17 changes in survivors' outcomes of depression, anxiety and summed severity of other symptoms are mediated by the intervening (week 13) state or caregivers' outcomes or potential covariates.

Exploratory Aim 4. The dyadic characteristics of responders will be compared to those of non-responders using t-tests, chi-square or Fisher's exact tests. Characteristics found to differ, along with mediators and other covariates listed in section C9d will be further considered as potential future tailoring variables. The decision rule (dd_1, dd_2) specifying the first and second intervention to achieve optimal outcome will be using the Qlearning optimization method^{258,270-272} implemented in SAS PROC QLEARN.^{273,274} The Q-learning algorithm proceeds backwards from the last decision to the first. Two Q-functions will be considered. The function $QQ_2(HH_2) = EE[YY_2|HH_2]$ is the expectation of the second stage outcome YY_2 given history after 2 stages, denoted by HH_2 : dyadic characteristics, outcomes observed during weeks 1-12, 13 and 17, and interventions received. The function $QQ_1(HH_1) = EE[YY_1 + \max QQ_2(HH_2)]$ uses history through the first intervention stage HH_1 . The conditional expectations in the Q-functions will be estimated from regression analyses for the primary outcomes, and the optimal decision rules will be found using backward induction by maximizing these functions.^{275,276} The product of this analysis will be identification of tailoring variables to operationalize the decision rules of selecting the optimal first intervention and switching from SMSH alone to TIP-C+SMSH. These personalized decision rules can then undergo testing in a future confirmatory RCT.

Potential Difficulties/Limitations and Alternative Approaches

Potential problems from recruitment and retention will be minimized by the use our previous methods yielding high retention rates with no differential attrition between conditions. Potential problems in intervention delivery will be minimized by implementing protocols to maintain intervention fidelity. There are no high-risk aspects of this trial, and all procedures are non-invasive. We recognize that in addressing depression and anxiety our efforts might inadvertently produce detrimental psychological responses. Should this occur, our experienced interventionists will refer the survivor and/or caregiver to mental health services. Because randomizations may not account for all possible error sources, we will adjust for baseline values of outcomes in the analysis to provide added control over possible confounding preintervention influences. Three primary outcomes (depression, anxiety, and summed severity of other symptoms) and all hypotheses are stated a priori. In the exploratory analyses, the Benjamini-Hochberg or Hochberg adjustment²⁷⁷⁻²⁷⁹ will be used to control the false discovery rate.

